17.6 Physical Examination

No summary table will be provided since physical examination findings during screening will be recorded as medical history events and findings during the trial as AEs.

17.7 Pregnancy test

Results of pregnancy test (serum and urine beta human chorionic gonadotropin for women only) will be listed.

17.8 B cell (CD19+) count

B cell (CD19+) count data will be listed by treatment group and time point (where applicable).

17.9 Urine Protein/Creatinine Ratio

Urine Protein/Creatinine Ratio data will be listed by treatment group and time point (where applicable).

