The Day 85 ACR50 and ACR70 proportions will be analyzed in the same way as the Day 85 ACR20 proportions.

Safety data will be listed and summarized using descriptive statistics.

In addition, efficacy and safety data collected during the open-label extension period will be summarized.

Pharmacokinetics

M2951 concentrations and PK parameters will be listed and summarized by trial day.

Pharmacodynamics

Data on immunoglobulin levels, **CCI** [REDACTED], and B cell numbers and subsets will be summarized in tabular and/or graphic format, as appropriate to the data. Potential PK/PD correlations may be explored and reported separately.

Table 1 Schedule of Assessments

Trial Period	Screening		Treatment Period						Optional Open-Label Extension Period				Safety Follow-up/ End of Trial Visit ^a
	1	2	3	4	5	6	7	8/End of Treatment ^b	9	10	11	12	
Trial Visit #	W1	W2	W3	W5	W7	W9	W13	85/Day 1 OLE	Day 14	Month 1	Month 3	Month 6	~28 days post last dose
Trial Week	-28 to -1	1	8	15	29	43	57						
Trial Day	-	-	+2	+2	+2	+4	+4		+2	+7	+7	+7	
Visit Window (days)								(X) ^b					
Informed consent	X												
Demographics	X												
RA and other medical history, medications history	X												
Inclusion/exclusion criteria	X	X											
Complete physical examination ^c	X		X					X		X		X	
Vital signs ^d	X	X	X	X	X	X	X	X		X		X	
12-lead ECG	X							X		X		X	
Chest X-ray ^e	X												
Concomitant medications ^f and procedures	X	X	X	X	X	X	X	X	X	X	X	X	
Hematology, chemistry (incl. LFTs) ^g	X	X	X	X	X	X	X	X	X	X	X	X	
Coagulation ^h	X												
Urinalysis, microscopy, urine protein/creatinine ratio	X		X	X				X		X		X	
Immunoglobulins ⁱ	X							X		X		X	
RF and anti-CCP ^j	X		X	X				X		X		X	
ESR ^j	X		X	X				X		X		X	
hsCRP ^k	X		X	X				X		X		X	
B cell numbers and subtypes ^l	X	X	X	X				X		X		X	
Viral serology ^m	X												

Trial Period	Screening	Treatment Period							Optional Open-Label Extension Period			Safety Follow-Up/ End of Trial Visit ^a	
		1	2	3	4	5	6	7	8/End of Treatment ^b	9	10	11	
Trial Visit #		W1	W2	W3	W5	W7	W9	W13					
Trial Week									Day 14				
Trial Day	-28 to -1	1	8	15	29	43	57	85/Day 1 OLE					
Visit Window (days)	-	-	±2	±2	±2	±4	±4		±2	±7	±7	±7	
Tuberculosis test ^m	X												
TSH	X												
Pregnancy test (serum β-hCG) ⁿ	X												
Urine pregnancy test ⁿ	X												
Pharmacokinetic sampling ^o	X												
CC1													

RA disease activity assessment ^r	X	X	X	X	X	X	X	X	X	X	X	X
Randomization	X											

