3.1 Potential Risks and Benefits

The safety assessments of M2951 rely on data accumulated during product development and from data on other BTK inhibitors. Based on the nonclinical and clinical data available to date, the conduct of the trial is regarded as justifiable at the planned dose.

M2951, is being considered for the treatment of autoimmune diseases, including RA, SLE, and MS. To date, no efficacy data are available. However, because its mechanism of action directly targets both the production of autoantibodies and cellular effectors of end-organ injury, it is reasonable to anticipate that M2951 may represent a significant advance in the treatment of RA and other autoimmune diseases.

No identified risks or new potential risks have emerged from the first-in-human trial, Trial EMR200527-001. M2951 was well tolerated [REDACTED]

Important potential risks to subjects are based on nonclinical safety data of M2951 and clinical data on adverse drug effects associated with compounds of a similar pharmacological class. They include infection, leukopenia, thrombocytopenia, hemorrhage, gastrointestinal intolerance, renal toxicity, hepatocellular injury, atrial fibrillation, drug-drug interactions, and embryofetal toxicity. It is unknown whether there are additive risks of cytopenias and elevated transaminases when M2951 is given with MTX; however, these potential risks will be readily monitored.

Risk minimization measures inherent to early phase clinical trials are considered adequate for the proposed clinical trial in RA patients. An IDMC will be set up to continually review available safety and tolerability data and will be mandated to make immediate decisions regarding the conduct of the trial; no additional risk minimization measures are proposed.

The dose of M2951 (50 mg bid) selected for the proposed trial is well within the dose ranges studied in Trial EMR200527-001 and showed high levels of target occupancy in healthy volunteers.

Taking the above information into account, benefit-risk considerations support conduct of the proposed clinical trial EMR200527-0081 in patients with RA.

For full details, refer to the latest IB for further information about the nonclinical and clinical programs and Guidance for the Investigator.

This clinical trial will be conducted in compliance with the clinical trial protocol, ICH GCP guidelines, and any additional applicable regulatory requirements.

4 Trial Objectives

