8.3.2 Secondary Endpoints

The key secondary endpoint is the percent change in hsCRP from Baseline to Day 29.

Other secondary endpoints (during the double-blind treatment period):

Efficacy:

- ACR50/ACR70 response at each time point assessed
- Percent change in hsCRP from Baseline to Day 85
- Change from Baseline in DAS28-hsCRP score at Day 29
- Change from Baseline in DAS28-hsCRP score at Day 85
- Percentage of subjects with DAS28-hsCRP < 3.2 (well-controlled disease) at Day 85
- Percentage of subjects with DAS28-hsCRP < 2.6 at Day 85
- Change from Baseline in ESR, anti-CCP, rheumatoid factor (at Days 29 and 85)
- Change from Baseline to Day 85 in subject's self-assessments including:
 - Global assessment of disease activity (VAS, see Section 7.3.1.1)

- Self-assessment of pain (VAS)
- Self-assessment of disability (HAQ-DI)
- Change from Baseline to Day 85 in Physician's Global Assessment of Disease Activity (VAS).

Safety:

- Nature, incidence and severity of TEAEs
- Change from Baseline in vital signs and 12-lead ECG data
- Change from Baseline in standard hematology and chemistry laboratory parameters including liver function tests, amylase/lipase, and urinalysis.

Pharmacokinetics and pharmacodynamics:

- Plasma concentrations of M2951 after administration on Day 1 and Day 29, PK parameters calculated for Day 1 and Day 29: AUC_{0-6h} , C_{max} , C_{pre} (Day 29), t_{max} , $R_{acc}(AUC_{0-6h})$, and $R_{acc}(C_{max})$. Further endpoints may be defined in the SAP.
- Absolute concentrations and change from Baseline in immunoglobulin levels (IgA, IgM, and IgG, and subclasses) on Day 29 and Day 85
- Absolute numbers and change from Baseline in B cell numbers and subsets on Day 85.

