8.5.5 Analysis of Safety and Other Endpoints

The analysis set for the safety assessments will be the Safety Analysis Set for the primary analysis and the OLE Safety Analysis Set for final analysis.

All safety endpoints will be summarized by treatment group unless otherwise specified. Analyses including both for the first 12-week treatment period and open-label extension period data will be summarized according to treatment groups 'M2951+MTX' and 'Placebo+MTX/M2951'.

Adverse events will be coded according to the Medical Dictionary for Regulatory Activities (MedDRA). The severity of AEs will be graded using NCI-CTCAE v4.03 toxicity grades (20). Adverse events with missing classification concerning IMP relationship will be considered related to the IMP.

The number and percentage of subjects experiencing 1 or more TEAEs will be summarized according to the MedDRA system organ classes and preferred terms by treatment group, relationship to IMP, and severity. Exposure-adjusted incidence rates of TEAEs will also be reported according to the MedDRA system organ class and preferred term.

Clinical laboratory parameters being monitored for safety will be summarized using descriptive statistics, by postdose shifts relative to Baseline for relevant parameters using relevant cutoffs as detailed in the SAP, box and whisker plots as relevant, and data listings of clinically significant abnormalities/outliers. Subject listings and summary statistics at each assessment time will be presented using the International System of Units (SI units).

Observed values and change from Baseline in vital signs and ECG data will be summarized for each treatment group using descriptive statistics. Clinically noteworthy physical examination, ECG, and CXR findings for individual subjects will be listed and summarized as appropriate.

At the end of the study, for final analysis, safety endpoints will be reported both for the first 12-week treatment period and for entire study, by treatment group, based on OLE Safety Analysis Set.

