17.3 Clinical Laboratory Evaluation

The following laboratory parameters will be measured during the trial as part of the safety evaluation:

- Hematology
- Biochemistry
- Urinalysis
- Coagulation

The clinical laboratory safety tests to be measured in this trial are provided in the protocol (refer to Section 7.4.3 Table 4 of the Clinical Trial Protocol [CTP]).

Continuous protocol-specified clinical laboratory findings (hematology, biochemistry, urinalysis, coagulation) will be summarized by treatment using descriptive statistics (see [Section 11](#)). The statistics will be presented for baseline, each time point during the study, and CFB to each time point, when applicable.

Laboratory results will be classified according to NCI-CTCAE Version 4.03 as provided by the central laboratory. In case a laboratory parameter has bi-directional toxicities (eg Potassium) both directions will be presented for the given parameter (ie Potassium Low and Potassium High). On-treatment values are results of assessments done from the first IMP administration on Day 1. Laboratory results containing a modifier such as “<” or “>=” will be handled case by case for summary statistics and will be reported as collected in the database in subject data listings.

A shift table of baseline versus post-baseline based on the worst NCI-CTCAE grade will be presented by treatment group for hematology and biochemistry.

Additional laboratory results that are neither classified in protocol nor part of NCI-CTCAE will be presented according to the categories based on normal ranges: below normal limits (Low), within normal limits (Normal), and above normal limits (High). Classification into categories will be presented in subject data listings only.

Boxplots of the laboratory values (by treatment arm) by time point will be provided for:

- Hemoglobin
- Absolute reticulocyte count
- White blood cell count
- Absolute neutrophil count
- Absolute lymphocyte count
- Platelet count
- Alanine aminotransferase (ALT)
- Aspartate aminotransferase (AST)
- Gamma-glutamyl transferase (GGT)
- Total bilirubin
- Amylase
- Lipase
- Creatinine
- Blood urea nitrogen (BUN)

Boxplots for laboratory parameters where toxicity grades are defined based on the ratio of the parameter values and the ULN will not be displayed using the unit of measurement but instead using the ratio of the measured value over ULN. This comprises the following parameters:

- ALT
- AST
- GGT
- Total bilirubin
- Creatinine
- Amylase

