17.10 Urinalysis Microscopic Evaluation

Urinalysis Microscopic Evaluation data will be listed by treatment group and time point (where applicable).

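### Urinary markers of renal injury have no by-arm summary in the SAP, so a renal signal confined to urine would appear only in listings

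*SAP*

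**What the plan says.** Protocol 3.1 lists the important potential risks, among them "gastrointestinal intolerance, renal toxicity, hepatocellular injury, atrial fibrillation". The schedule of assessments (protocol Table 1) has a row for "Urinalysis, microscopy, urine protein/creatinine ratio", done at Screening and repeated later. Protocol Table 4 includes dipstick protein and blood, microscopy and, as a separate entry, spot urine protein and creatinine among the safety laboratory tests. SAP 17.3 points to that table for its own scope.

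Protocol 8.3.2 sets as a safety endpoint "Change from Baseline in standard hematology and chemistry laboratory parameters including liver function tests, amylase/lipase, and urinalysis", and 8.3.4 repeats it for the open-label extension. Protocol 8.5.5 says that laboratory parameters monitored for safety are to be summarised, among other ways "by postdose shifts relative to Baseline for relevant parameters using relevant cutoffs as detailed in the SAP".

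The SAP provides the following for urine:

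- Section 17.9: "Urine Protein/Creatinine Ratio data will be listed by treatment group and time point (where applicable".
- Section 17.10: "Urinalysis Microscopic Evaluation data will be listed by treatment group and time point (where applicable".
- Section 17.3 gives by-treatment descriptive statistics for continuous findings only, and then: "A shift table of baseline versus post-baseline based on the worst NCI-CTCAE grade will be presented by treatment group for hematology and biochemistry". No urine parameter is in its boxplot list. Results that neither the protocol nor CTCAE classifies are put into low, normal or high categories in listings only.

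SAP Section 9, which records changes from the protocol's planned analyses, says nothing about urine results.

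**The concern.** The protocol names a renal risk, schedules urine tests that bear on it, and promises a summary of safety laboratory results. The SAP then gives the protein/creatinine ratio and microscopy no summary at all, and leaves categorical dipstick results outside both of its laboratory tables.

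At stake is a moderate shift in proteinuria or hematuria on M2951 that comes without a creatinine rise and without a reported adverse event. Followed as written, the SAP would produce no figure by arm for it. A reader would have to find the pattern by going through individual listings for about 64 subjects.

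**Working it through.** The plan states no figure on this point, so the main check sets the renal measures against their specified outputs.

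| Measure | By-arm output in the SAP | Where |
|---|---|---|
| Serum creatinine | Descriptive statistics with change from baseline; worst-grade shift table; boxplots | 17.3 |
| Blood urea nitrogen | Descriptive statistics with change from baseline; boxplots | 17.3 |
| Renal and urinary TEAEs | Tables by SOC and PT, worst grade and relationship; exposure-adjusted rates | 17.1.1 |
| Continuous urinalysis items | Descriptive statistics | 17.3 |
| Dipstick protein and blood (if categorical) | None specified | 17.3 |
| Spot protein/creatinine ratio | None; listing | 17.9 |
| Urine microscopy | None; listing | 17.10 |

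The last three rows are the gap. Two provisions might close it, and neither does so clearly.

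1. The protein/creatinine ratio is continuous and could be read as part of urinalysis in SAP 17.3. But protocol Table 4 keeps spot urine separate from urinalysis, and SAP 17.9 deals with the ratio specifically and calls only for a listing.
2. SAP Section 11 says that qualitative variables get counts and percentages. But SAP 17.3 applies Section 11 only to continuous laboratory findings.

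One contrast within the SAP is useful. Protocol 7.4.4.3 schedules the chest X-ray only at Screening, so it cannot show a drug effect, yet SAP 17.11 tabulates it by treatment group. The on-treatment protein/creatinine ratio is not tabulated.

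A second check asks whether a by-arm summary would be informative at this sample size. Inputs: 64 subjects randomised 1:1, so 32 per arm; the plan's 2-sided 80% interval, borrowed from the efficacy analysis, with normal quantile 1.2816; and an SD of the log ratio of 0.5 to 1.0, which is an assumption because the documents give none.

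- Standard error of the difference in mean log ratio = SD × sqrt(2/32) = SD × 0.25.
- Multiplicative half-width = exp(1.2816 × SD × 0.25).
- SD 0.5: exp(0.160) = 1.17. SD 0.8: exp(0.256) = 1.29. SD 1.0: exp(0.320) = 1.38.

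For a true 1.5-fold between-arm difference, the chance that the lower 80% limit lies above 1 is Φ(ln 1.5 / (0.25 × SD) − 1.2816), with ln 1.5 = 0.405.

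- SD 0.8: Φ(2.03 − 1.28) = Φ(0.75), about 77%.
- SD 1.0: Φ(1.62 − 1.28) = Φ(0.34), about 63%.

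The collected data would therefore be informative, but at the upper end of the assumed SD range they would not reliably establish a 1.5-fold rise.

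**The case against.** A reader might infer that renal safety is never compared between arms, or that creatinine is the only renal measure tabulated. The documents do not support either. Creatinine, blood urea nitrogen and renal TEAEs all have by-arm outputs.

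A reader might also argue that a creatinine doubling from 0.5 to 1.0 × ULN would be hidden because the boxplots use the ratio to ULN. That is true of the boxplot alone. Change from baseline is summarised by arm at each time point. Protocol Table 3 places more than 1.5 to 3 times Baseline in Grade 2, and SAP Section 9 identifies only that table's Grade 1 entries for creatinine as wrong, so the doubling should also reach the by-arm shift table. Nor do the documents say whether creatinine responds later than urine markers, so the point cannot rest on timing.

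The stronger objections are these:

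- **The protocol left the choice to the SAP.** Protocol 8.5.5 promises shifts only for relevant parameters and also mentions listings of clinically significant abnormalities. SAP 17.3 does list out-of-range urinalysis values. This stands as to shifts: omitting a urine shift table breaks no explicit promise. It does not answer the absence of any summary for a stated endpoint.
- **Adverse event reporting is a backstop.** Under protocol 6.5.4, a laboratory change to a higher severity grade leads to interruption and recheck, and an abnormality that leads to discontinuation is reportable as an AE. SAP 17.1.1 tabulates such events. This stands in part. Under protocol 7.4.1.1 an abnormal result is otherwise an AE only if it has clinical signs and symptoms or the Investigator judges it medically important. Isolated, ungraded or transient urine findings can escape.
- **The IDMC sees unblinded safety data.** Its outputs are defined in a separate SAP that was not available for this review. Whatever it contains, the analyses for the clinical study report are governed by the present SAP.

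**Conclusion.** The point holds as a limited gap in the safety outputs. The SAP specifies no by-arm summary for the spot protein/creatinine ratio, for dipstick protein and blood, or for microscopy. This falls short of protocol 8.3.2 and of the general promise in 8.5.5 for a named potential risk, and Section 9 does not declare it. The consequence is confined to a signal seen in urine alone.

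The conclusion on dipstick results assumes that they are reported as categories, which the documents do not state. The interval widths rest on the assumed SD and show only that a summary would be worth having. They are not an argument for formal testing, since safety analysis in this plan is descriptive. The primary efficacy analysis is not affected.

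**What to change.** Amend the SAP in three places.

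1. **Section 17.9:** replace the listing-only rule with by-arm, by-visit summaries of the protein/creatinine ratio and of its ratio to baseline, using geometric means and the baseline definition in SAP Section 11. Keep the listing.
2. **Section 17.3:** add a by-arm shift table from baseline to worst post-baseline value for dipstick protein, dipstick blood, and the protein/creatinine ratio against the laboratory's normal limit.
3. **Section 17.10:** add a by-arm count of subjects with abnormal post-baseline microscopy. A shift table would not work here: protocol Table 4, footnote d, makes microscopy conditional on an abnormal dipstick for blood, protein or nitrite, so many subjects would have no baseline result.

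The comparison with placebo belongs to the primary (12-week) analysis. In the final analysis all subjects receive M2951 in the extension, so the same tables there are descriptive. If the sponsor prefers to keep listings only, Section 9 should say so and give the reason.

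The cost is SAP wording and a few extra tables from data already collected. No new samples or visits are needed, and no clinical rule changes.

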17.10 Urinalysis Microscopic Evaluation

Urinalysis Microscopic Evaluation data will be listed by treatment group and time point (where applicable).

17.11 Chest X-ray evaluations

CXR evaluations will be listed and tabulated by treatment group using the number and percentage of subjects for each interpretation category (Normal, Abnormal Not Clinically Significant, Clinically Significant, and Abnormal Overall).

19.1 Appendix 1: HAQ-DI scoring

The HAQ-DI is a subject-reported questionnaire that consists of 24 questions referring to 8 domains: dressing and grooming, arising, eating, walking, hygiene, reach, reach, grip, and activities.

The questionnaire scores the subject's self-perception (20 questions): 0=without any difficulty, 1=with some difficulty, 3=unable to do, and reports use of special aids or devices and/or the need for assistance from another person:

Domains	Questions
Dressing and grooming	1. Dress yourself, including tying shoelaces and doing buttons? 2. Shampoo your hair?
Arising	3. Stand up from a straight chair? 4. Get in and out of bed?
Eating	5. Cut your meat? 6. Lift a full cup or glass to your mouth? 7. Open a new milk carton?
Walking	8. Walk outdoors on flat ground? 9. Climb up five steps?
	Check any aids or devices that you usually use for any of the above activities (questions 1 to 9): Devices used for dressing (button hook, zipper pull, etc.) / Special or built up chair / Built up or special utensils / Cane / Walker / Crutches / Wheelchair / Other
	Check any categories for which you usually need help from another person (questions 1 to 9): Dressing and grooming / Arising / Eating / Walking
Hygiene	10. Wash and dry your body? 11. Take a tub bath? 12. Get on and off the toilet?
Reach	13. Reach and get down a 5 pound object (such as a bag of sugar) from just above your head? 14. Bend down to pick up clothing from the floor?
Grip	15. Open car doors? 16. Open jars which have been previously opened? 17. Turn faucets on and off?
Activities	18. Run errands and shop? 19. Get in and out of a car? 20. Do chores such as vacuuming or yard work?
	Check any aids or devices that you usually use for any of the above activities(questions 10 to 20): Raised toilet seat / bathtub seat / bathtub bar / long-handled appliances in bathroom / long-handled appliances for reach / jar opener (for jar previously opened) / Other
	Check any categories for which you usually need help from another person (questions 10 to 20): Hygiene / Reach / Gripping an opening things / Errands and Chores

The highest score for any component question of each of the eight domains determines the score for that domain. Each domain must have at least one question answered. Otherwise, the domain score is set to missing.

The non-missing domain scores are adjusted, based upon the patient's use of any aid, device or assistance (multiple aids, devices, or assistance could be checked). The relationship between aids, devices help from another person and the disability domain is shown below:

Domains	Aids or devices	Help from another person
Dressing and grooming	Devices used for dressing / Other	Dressing and grooming
Arising	Special or built up chair / Other	Arising
Eating	Built up or special utensils / Other	Eating
Walking	Cane / Walker / Crutches / Wheelchair / Other	Walking
Hygiene	Raised toilet seat / bathtub seat / bathtub bar / long-handled appliances in bathroom / Other	Hygiene
Reach	long-handled appliances for reach / Other	Reach
Grip	jar opener / Other	Gripping an opening things
Activities	Other	Errands and Chores

If either aid or device and/or help from another person are checked for a domain or 'other' aid/device/assistance was needed, then the score for that domain is raised from 0 or 1 to 2 and unchanged if already scored at 2 or 3. If no aid, device and assistance were needed, the score for that domain will remain as raw score.

The disability index is the mean of the eight domain scores. If at least two of the domains are missing, the disability index cannot be obtained. If fewer than 2 of the domain scores is missing, divide the sum of the domains by the number of answered domains. The disability scores between 0 and 3, with higher score indicating greater disability.

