7.3.1.4 Health Assessment Questionnaire – Disability Index (HAQ-DI)

The HAQ-DI is a subject-reported questionnaire that is commonly used in RA to measure disease-associated disability (assessment of physical function). It consists of 24 questions referring to 8 domains: dressing/grooming, arising, eating, walking, hygiene, reach, grip, and activities (24-26).

The disability section of the questionnaire scores the subject's self-perception on the degree of difficulty (0 = without any difficulty, 1 = with some difficulty, 2 = with much difficulty, and 3 = unable to do) covering the following domains: dressing and grooming, arising, eating, walking, hygiene, reach, grip, and performing other daily activities. The reported use of special aids or devices and/or the need for assistance of another person to perform these activities is also assessed. The scores for each of the functional domains will be averaged to calculate the functional disability index.

Validated translated versions of the HAQ-DI will be used for each country participating in this trial.

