16.1 Primary Endpoint Analyses

The primary endpoint, ACR20 response rate at Week 12, will be presented on the mITT Analysis Set.

The ACR20 is a primary efficacy measure for which, at Week 12, a subject must have at least 20% improvement in the following ACR Core Set values.

- TJC (being the number of joints assessed as “Pain/Tender only” or “Pain/Tender and Swollen” among the 68 joint count) and
- SJC (being the sum of joints assessed as “Swollen only” or “Pain/Tender and Swollen” among the 66 joint count) and
- An improvement of at least 20% in at least 3 of the following 5 assessments:
 - Subject’s Global Assessment of Disease Activity
 - Subject’s Assessment of Pain

- Subject's Assessment of Physical Function as measured by the HAQ-DI
- Physician's Global Assessment of Disease Activity
- Acute phase reactant as measured by hsCRP.

In this trial, ACR20 response calculations will use the HAQ-DI for the subject's assessment of physical function and hsCRP as the measure of acute phase reactant.

Improvement of at least 20% of these assessments is defined as follows:

- TJC (68 joint count): a decrease of at least 20% of the number of tender joint compared to baseline
- SJC (66 joint count): a decrease of at least 20% of the number of swollen joint compared to baseline
- Subject's Global Assessment of Disease Activity: a decrease of at least 20% on the VAS compared to baseline.
- Subject's Assessment of Pain: a decrease of at least 20% on the VAS compared to baseline.
- Subject's Assessment of Physical Function: a decrease of at least 20% of the HAQ-DI score compared to baseline.
- Physician's Global Assessment of Disease Activity: a decrease of at least 20% on the VAS compared to baseline
- Acute phase reactant: a decrease of at least 20% of hsCRP measurement compared to baseline

The hypotheses tested are as follows:

- H0: Difference in ACR20 response rates at Week 12 (M2951 versus placebo) ≤ 0 .
- H1: Difference in ACR20 response rates at Week 12 (M2951 versus placebo) > 0 .

Tests will be based on the 2-sided 80% CI for Δ .

The Week 12 ACR20 proportion and a 2-sided 80% CI will be provided for each treatment group. The difference Δ in ACR20 proportions between M2951 + MTX and placebo + MTX, and a 2-sided 80% CI for Δ , based on the "corrected Miettinen-Nurminen" method (3) - method of Mee interval corrected with Miettinen and Nurminen factor $n/(n-1)$, n being the total number of evaluable randomized subjects - will be provided.

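### As written, one tick in a shared *Other* aid box raises up to four HAQ-DI domains to 2, moving the index by up to 1.00 and the HAQ component of ACR response with it

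*SAP*

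**What the plan says.** SAP 19.1 scores each of eight HAQ-DI domains as its highest item, adjusts the domain for aids or help, and takes the mean of the eight.

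Aids are collected in two checklists. The first covers questions 1 to 9 (dressing, arising, eating, walking) and is introduced by "Check any aids or devices that you usually use for any of the above activities (questions 1 to 9"; its entries end "Built up or special utensils / Cane / Walker / Crutches / Wheelchair / Other". The second covers questions 10 to 20 (hygiene, reach, grip, activities) and also ends in a single *Other*. The text shows no field for specifying the aid.

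A mapping table then links aids and help to domains, with *Other* against all eight. Under the rule that follows, where an *Other* "aid/device/assistance was needed, then the score for that domain is raised from 0 or 1 to 2", and a domain is "unchanged if already scored at 2 or 3".

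The same appendix prints the item scale as "0=without any difficulty, 1=with some difficulty, 3=unable to do". Protocol 7.3.1.4 prints "0 = without any difficulty, 1 = with some difficulty, 2 = with much difficulty, and 3 = unable to do".

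HAQ-DI is one of the five assessments of which three must improve for ACR20 (Protocol 7.3.1.1, SAP 16.1). Its criterion is "a decrease of at least 20% of the HAQ-DI score compared to baseline". It also feeds ACR50 and ACR70, and it is a secondary endpoint (SAP 16.2.2) and an extension endpoint (SAP 16.3.1).

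**The concern.** The mapping table exists to tie each aid to the domain it bears on, and for every named aid and every help category it does so one to one. Only *Other* breaks the pattern. A tick in that box identifies no domain, yet the table attaches it to all four domains of its checklist.

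A subject who ticks *Other* therefore carries a floor of 2 in four domains, whatever the aid is for. While the tick stays, improvement below 2 in those domains is invisible. When the tick appears or disappears between visits, the index can jump by much more than one aid would otherwise move it. HAQ-DI can be the deciding assessment for ACR20. With about 60 subjects randomised 1:1 (SAP 7), one reclassified responder moves an arm's rate by 1/30, or 3.3 percentage points.

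**Working it through.** **Inputs.** From SAP 19.1: raw domain score = highest item; index = sum of the eight domain scores / 8; an *Other* tick sets each of the four domains in its checklist to max(raw, 2), on the literal reading. From SAP 16.1 and 16.2.2: the HAQ component needs a fall of at least 20%, 50% or 70% from baseline.

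**The plan's own figure.** The appendix gives an index range of 0 to 3. All domains at 0 give 0/8 = 0.0 and all at 3 give 24/8 = 3.0, so the coded rule reproduces it.

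**Shift from a tick.**

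| Raw domains | No tick | One *Other* tick | Both ticks |
|---|---|---|---|
| all 0 | 0.00 | (4×2 + 4×0)/8 = 1.00 | 8×2/8 = 2.00 |
| all 1 | 1.00 | (4×2 + 4×1)/8 = 1.50 | 8×2/8 = 2.00 |

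One tick thus adds up to 1.00. Tied to a single domain it would add at most 2/8 = 0.25 (domain at 0), or 1/8 = 0.125 (domain at 1). Domains already at 2 or 3 do not move.

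**Masking.** Baseline raw 1 in all domains; by Week 12 two domains fall to 0. Raw: 8/8 = 1.00 to 6/8 = 0.75, a 25% improvement, so the ACR20 component is met. If both improving domains lie in a checklist ticked at both visits, the adjusted score is 1.50 to 1.50, or 0%, and the component is lost. Under single-domain attribution the result depends on where the aid belongs. If it belongs to a domain that did not improve, the score is 9/8 = 1.125 to 7/8 = 0.875, or 22% (met). If it belongs to one of the two that did, it is 1.125 to (2 + 0 + 6)/8 = 1.00, or 11% (not met).

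**Creation.** Raw 1 in all domains at both visits, with one tick at baseline and none at Week 12: 1.50 to 1.00, and 0.50/1.50 = 33%, so the ACR20 component is met with no change in any item. Under single-domain attribution: 1.125 to 1.00, and 0.125/1.125 = 11%, not met.

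**Both boxes ticked at Week 12.** The index cannot fall below 2.00. The largest possible improvement is (3.00 − 2.00)/3.00 = 33%, so the HAQ component of ACR50 and ACR70 is unattainable. The ACR20 component needs a baseline of at least 2.00/0.80 = 2.50.

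**Carry-through to ACR20.** Response needs both joint counts plus three of five assessments. HAQ-DI decides the result only when both joint-count criteria are met and exactly two of the other four assessments are met.

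**Response level 2.** The SAP list lacks it, but the protocol has "2 = with much difficulty", and the SAP's own adjustment rule allows for domains already at 2. Restoring the level changes none of the figures above.

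**The case against.** Several answers to this point carry weight.

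- **The scoring source is unseen.** The protocol says only that aids and assistance are assessed and gives no allocation rule for *Other*; the HAQ references that both documents cite are not reproduced. A reader might infer that the SAP departs from the correct HAQ scoring. The documents do not show that. They do show that the SAP's mapping treats *Other* unlike every other entry.
- **The rule is phrased per domain.** The table could be read as listing what may count for each domain. That reading is possible, but a single tick per checklist gives a programmer nothing with which to choose the domain.
- **An unlisted aid may serve several activities.** It cannot be assumed that *Other* belongs to only one domain, so a fix should allow more than one.
- **Dropping a tick may be real change.** Aid use is part of what the instrument measures, and a named aid such as a cane also sets a floor of 2. It would go too far to call the 33% improvement false. The objection is to its size: four domains move on one unspecified aid.
- **The missing level 2.** A reader might infer that answers at that level would be mis-scored. They would not: the protocol lists it and the SAP's adjustment rule expects it.
- **Limited reach.** The rule is the same in both arms under blinding, so no directional bias follows. HAQ-DI change as a secondary endpoint receives only summary statistics (SAP Table 12). A reader might infer that affected subjects fail ACR20 or ACR50. Only the HAQ component fails, and three of the other four assessments suffice without it.

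**Conclusion.** The concern stands as a defect in a stated scoring rule. As written, one *Other* tick can raise four domains and shift HAQ-DI by up to 1.00, four times the 0.25 maximum under single-domain attribution. That is enough to lose or gain the 20% HAQ component, and with both boxes ticked at Week 12 it puts the 50% and 70% components out of reach.

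This rests on the literal reading of the mapping table. The examples show what the rule can do, not what is typical. The share of subjects ticking *Other*, and how often ticks change between visits, are not given, so neither the number affected nor any effect on the ACR20 comparison can be computed. The omission of level 2 is a separate drafting slip with no consequence for results.

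**What to change.** Before the treatment codes are broken for the Week 12 analysis, amend SAP 19.1 as follows.

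1. Remove *Other* as an automatic trigger for every domain of a checklist. If a specification of the aid was collected, let *Other* raise only the domain or domains to which blinded review assigns it. If none was collected, or the aid cannot be assigned, leave the raw score. Adjustments for named aids and for help from another person stay as they are.
2. Report the ACR responses and HAQ-DI under the as-written rule as a sensitivity analysis.
3. As a clerical correction, print level 2 in the response scale to match Protocol 7.3.1.4.

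The cost is appendix wording, one programming rule, one additional set of outputs and, where specifications exist, a short blinded review. The downside is that unassignable aids receive no adjustment. It is sharpest for Activities, whose only listed aid is *Other*: without a specification, that domain would be adjusted only through help from another person.
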